12.2. Laboratory Evaluations

Safety laboratory samples for chemistry, hematology, and urinalysis will be collected at various visits. Refer to Section 9 of the Protocol for the schedule of activities indicating when the respective samples are taken.

The following parameters will be included:

Chemistry: Albumin, Alanine aminotransferase, Alkaline phosphatase, Aspartate aminotransferase, Blood urea nitrogen or urea, Creatinine, Electrolytes (sodium, potassium, chloride, calcium, phosphorus), Gamma glutamyltransferase, Lactate dehydrogenase, Total bilirubin, Direct bilirubin, and total Immunoglobulin E.

Hematology: Full and differential blood count, Hematocrit, Hemoglobin, Mean cell hemoglobin, Mean cell hemoglobin concentration, Mean cell volume, Platelet count, Red blood cell count (% reticulocytes), White blood cell count with differential (neutrophils, lymphocytes, monocytes, eosinophils, and basophils).

Urinalysis: Appearance, pH, Protein, Glucose, Ketone bodies, Indicators of blood and white blood cells, Specific gravity, Urine human chorionic gonadotropin (premenopausal females only), and Urobilinogen.

Serology: HIV antibody, Hepatitis B virus, Hepatitis C virus, Hepatitis C virus RNA, Hepatitis B surface antigen, Hepatitis B core antibody, Hepatitis B surface antibody, and Follicle-stimulating hormone (confirmatory test for female patients in a postmenopausal status defined as cessation of menses for at least 12 months without an alternative medical cause).

Pregnancy test: A serum pregnancy test will be performed on all women of childbearing potential at Screening, and a urine pregnancy test will be performed at all other visits. Refer to Section 9 of the Protocol for the schedule of activities indicating when the respective pregnancy tests are performed.

All summaries will be based on results in SI (standard international system of units) units and will be output in the order listed above.

Actual values and changes from baseline in chemistry and hematology will be summarized by visit using descriptive statistics.

12.3. Vital Signs

Heart rate (beats per minute [bpm]), respiratory rate (breaths per minute), systolic and diastolic blood pressure (mmHg), BMI (kg/m²)_and body temperature (degree Celsius) will be measured at different visits as per the SoA in Protocol Section 9.

The conversion for temperature is as follows: Temperature (in °C) = 5/9 (Temperature [in °F]-32).

Actual values and changes from baseline in vital sign measurements will be summarized by visit using descriptive statistics.

All vital signs will be provided in data listings.

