### 4.3.2 Monitoring of Cardiovascular, Psychiatric, Hepatic, and Metabolic Risks

In the unblinded phase 2 trial UNI50001-203 (under reporting) in psoriasis, seven cases of elevated ALT were observed, and one patient in the orismilast 40 mg group had self-injurious behavior without suicidal intent at week 16. No deaths or serious infections were reported in UNI50001-203. Hepatic laboratory parameters will be monitored. All patients will be monitored for any cardiovascular manifestations using vital signs and 12-lead ECG at scheduled visits. Drug class potential effects, such as weight loss and major depression, will be monitored during the study. Patients with major depression, presenting major psychiatric disorders or at risk for suicide will be excluded from enrollment, and suicidal ideation and depressive symptoms will be assessed in the course of the study by the Columbia-Suicide Severity Rating Scale (C-SSRS) and Hospital Anxiety and Depression Scale (HADS), respectively. Patients will be informed of the potential increased risk of depression or suicidal thoughts of this class of drugs, and recommended to promptly contact their study doctor in case of such event.

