#### 11.2 Vital Signs and Body Weight

Vital signs (body temperature [measured in the ear], respiration rate, heart rate, and systolic and diastolic blood pressure measurements) will be evaluated at the visits indicated in the Schedule of Assessments (Table 4). All vital signs will be measured after the patient has been resting in a sitting position for at least 5 minutes. Blood pressure measurements are to be taken in the same arm for the duration of the study. Body weight (without shoes) will be recorded whenever vital signs are recorded; height (without shoes) will be recorded at Baseline only. A weight reduction of least 5% from baseline should be reported as a TEAE.

Vital sign measurements will be repeated if clinically significant or machine/equipment errors occur. Out-of-range blood pressure, respiratory rate, or heart rate measurements will be repeated at the Investigator's discretion. Any confirmed, clinically significant vital sign measurements must be recorded as AEs on the eCRF.

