5.5. Safety Endpoints

• The occurrence, severity, and seriousness of treatment-emergent AEs (TEAEs) reported over the 16week Treatment Period and the 4-week Follow-up Period.

- Changes from Baseline in physical examination findings; vital signs measurements (body temperature, respiration rate, heart rate, and systolic and diastolic blood pressure measurements); and body weight over the 16-week Treatment Period and the 4-Week Follow-up Period.
- Clinically significant abnormal changes in ECG findings over the 16-week Treatment Period.
- Changes from Baseline in safety laboratory values (hematology, serum chemistry, and urinalysis) over the 16-week Treatment Period.
- Change from Baseline in HADS score at each visit except Week 1.
- C-SSRS score at each visit except Week 1.

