12.1. Adverse Events

AEs for all patients in the safety population will be included in the AE summaries.

Adverse events will be summarized by system organ class (SOC) and preferred term (PT) for each treatment and Orismilast total, based on the MedDRA dictionary version 24.0. Severity of AEs will be graded according to National Cancer Institute (NCI) Common Terminology Criteria for Adverse Events (CTCAE) version 5.

Any AEs that occur before dosing on study Baseline will be categorized as pretreatment events. TEAEs will be defined as those AEs that occur or worsen in severity after initial dosing and up to 7 days after the last dose of study drug.

Duration will be calculated for AEs that resolve as the difference between the resolution date and onset date plus 1 and expressed in days.

The summary tables will include the number of patients and the number of events. Percentages will be based on the number of patients in the safety population. For summaries by SOC and PT, a patient will be counted once at the SOC level and once at each PT within the SOC level.

For summaries by SOC, PT, and maximum severity, a patient will be counted once at the highest severity level for which the event occurred at the SOC level and the highest severity level for each unique PT within that SOC level. Therefore, patients may only contribute once to each PT and once to each SOC level.

The summaries presenting frequency of AEs by SOC and PT will be ordered by Orismilast total descending frequency of SOC and then, within a SOC, by Orismilast total descending frequency of PT.

The following tables will be provided:

- An overall summary of the number of events and number and percentage of patients reporting TEAEs, related TEAEs (TEAEs recorded as "Relationship to study drug" = "Possibly" or Probably" or "Definitely"), serious TEAEs (TESAEs), TEAEs resulting in death, TEAEs of special interest, TEAEs leading to study drug discontinuation, TESAEs leading to study drug discontinuation, TEAEs by relationship and TEAEs by toxicity grade (including exposure adjusted incidence rates [EAIR]);.A similar summary will be presented starting within the dose titration period (initial 3 weeks)." (without EAIR).
- TEAEs overall by system organ class and preferred term (including EAIR);
- TEAEs overall by system organ class and preferred term starting within the dose titration period (initial 3 weeks)
- TEAEs by maximum toxicity grade, overall and by system organ class and preferred term;

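### Change in body weight is a named safety endpoint, but the SAP specifies no post-baseline summary of measured weight and no count of losses of at least 5%

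*SAP*

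**What the plan says.** **Endpoint.** Protocol 5.2.3 and SAP 5.5 both list, among the changes from baseline to be evaluated, physical examination findings, vital signs "and body weight over the 16-week Treatment Period and the 4-Week Follow-up Period". The vital signs are enumerated in parentheses, and weight is named separately after them.

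**Why it is monitored.** Protocol 4.3.2 says: "Drug class potential effects, such as weight loss and major depression, will be monitored during the study".

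**Collection.** Protocol 11.2 says: "Body weight (without shoes) will be recorded whenever vital signs are recorded". Height is measured once, at Baseline. Table 4 has separate rows for weight and BMI.

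**Reporting threshold.** Protocol 11.2 adds: "A weight reduction of least 5% from baseline should be reported as a TEAE".

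**Planned analysis.** SAP 12.3 lists heart rate, "respiratory rate (breaths per minute), systolic and diastolic blood pressure (mmHg), BMI" and body temperature, and then states: "Actual values and changes from baseline in vital sign measurements will be summarized by visit using descriptive statistics". The SAP index of tables has one vital-signs summary, Table 14.3.4.4.1, whose title names no parameters. It has no table for weight. SAP 8.3 summarises body weight at baseline only.

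**The concern.** The analysis section does not match the endpoint section. SAP 12.3 gives an explicit list of parameters, and a programmer working from it would produce BMI and not weight. SAP section 14, which lists changes from the protocol, does not mention dropping weight, so this looks like an oversight and not a decision.

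Dose selection for Phase 3 is a secondary objective, and weight loss is a class effect that the protocol itself singles out. If weight loss rose with dose, the natural evidence would be measured weight by visit and arm, together with the number of patients passing the protocol's 5% mark. The SAP specifies neither after baseline.

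**Working it through.** The plan states no figure on this point, so the check compares the schedule with the specified analysis.

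**1. Visits.** From Table 4 of the Protocol:

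| | Day 1 | W4 | W8 | W12 | W16 | W20 |
|---|---|---|---|---|---|---|
| Weight | yes | yes | yes | yes | yes | yes |
| BMI | yes | no | yes | no | yes | yes |

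There are 5 post-baseline weight visits and 3 post-baseline BMI visits. The difference is Weeks 4 and 12, which is 2/5 = 40% of the scheduled post-baseline weights. Week 4 is also the first weight taken after titration.

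**2. What BMI carries.** With height h fixed at its baseline value, BMI = W/h². Hence

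(BMI_t − BMI_0)/BMI_0 = (W_t − W_0)/W_0.

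Percent change in BMI equals percent change in weight. SAP 12.3, however, plans actual values and absolute changes only. The absolute BMI change that corresponds to a 5% loss is 0.05 × W_0/h², which depends on the patient. The documents give no distribution of height or weight, so I assume heights of 1.60 to 1.90 m and weights of 50 to 110 kg:

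- smallest: 0.05 × 50/1.90² = 2.5/3.61 = 0.69 kg/m²
- largest: 0.05 × 110/1.60² = 5.5/2.56 = 2.15 kg/m²

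The same 5% loss is therefore a BMI fall of about 0.7 to 2.2 kg/m². A mean BMI change by arm cannot be turned into a count of patients who lost 5%.

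**3. What the adverse-event tables carry.** A loss of at least 5% is to be reported as a treatment-emergent event, and SAP 12.1 tabulates these by system organ class and preferred term. Three limits apply:

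- The investigator must compute the percentage and report the event.
- A preferred term does not isolate the 5% threshold.
- Treatment-emergent events are those that "occur or worsen in severity after initial dosing and up to 7 days after the last dose of study drug". Week 20 is nominally 28 days after Week 16. For a patient who completes treatment, a loss first seen at Week 20, with onset dated to that visit, falls outside the 7 days and goes to the separate follow-up table.

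Weight loss is also not named among the events of special interest in Protocol 11.8.2, so no special-interest table is set to single it out.

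**4. How the SAP treats comparable risks.** SAP 12.4 counts patients over QTc thresholds at each visit and at any time. SAP 12.2 has a liver safety table. SAP 12.6 gives category and shift tables for depression, which Protocol 4.3.2 names in the same sentence as weight loss. Weight has a numeric threshold in the protocol but no threshold table.

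**The case against.** The strongest reply is that the data are not lost and much of the signal would be seen.

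- **BMI tracks weight.** With height fixed, BMI change is weight change divided by a constant. It is summarised at Week 16, the end of treatment, and at Week 20, the end of follow-up. A reader might infer that the plan gives no result at all on weight. That goes too far: a dose-related mean loss could show in BMI at three visits. What stands against BMI is the gap at Weeks 4 and 12 and the missing threshold count.
- **Losses of 5% have a reporting route.** A reader might infer that they would never be tabulated, or would depend on spontaneous reports. The documents do not support either. Protocol 11.2 directs the reporting at a stated threshold, from weights measured at scheduled visits including Weeks 4 and 12, and SAP 12.1 tabulates the events. The route is weaker than a count from the measurements, but it exists.
- **The output may already include weight.** SAP 7.1 promises listings and summary tables in general terms, Protocol 11.2 treats vital signs and weight together, and the shells are separate. A weight row in Table 14.3.4.4.1 is possible. An unseen shell still does not prespecify the parameter, visits or threshold, and SAP 12.3 as written points the other way.
- **The 5% count is not an endpoint.** This is correct: the endpoint is change in weight, and 5% is a reporting rule. The count is recommended as a better method than relying on investigator calculation and coding. Its absence is not itself a breach of the plan.

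**Conclusion.** The point holds for post-baseline summaries of measured weight. A named safety endpoint has no specified analysis after baseline. At 2 of 5 post-baseline visits (40%) neither weight nor BMI is set to be summarised. No table specified in the SAP counts losses of at least 5% from measured weights.

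The consequence is confined to descriptive safety reporting. SAP section 12 plans no inference on safety data, and no efficacy result, significance level or analysis population is affected. It is still worth correcting before the tables are programmed, because weight loss is an expected class effect and the trial is meant to inform the choice of dose.

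The conclusion assumes that the SAP 12.3 list is complete as written and that BMI is summarised only where Table 4 schedules it. If the shells already contain weight by visit, what remains is to align the SAP text and add the threshold count. The BMI range of 0.7 to 2.2 kg/m² rests on assumed heights and weights and is illustrative only.

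**What to change.** 1. Add body weight (kg) to the SAP 12.3 parameter list and to Table 14.3.4.4.1, with actual value, change and percent change from baseline at Weeks 4, 8, 12, 16 and 20, by treatment arm. SAP 7.2 already defines both change formulas.
2. Add the number and percent of patients with at least 5% loss from baseline, computed from measured weights, at each visit and at any time post-baseline, by arm. The threshold is the protocol's own reporting mark, and the layout can follow the QTc counts in SAP 12.4.
3. Check the shells against the revised text.

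The cost is a sentence or two in the SAP and a few rows in an existing table. The weights are already collected, so no visit, procedure or case report form changes.

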12.4. ECG

A 12-lead, resting ECG will be obtained at the visits indicated in the SoA in Protocol Section 9.

Actual values and changes from baseline in ECG parameters (heart rate [bpm], PR Interval [msec], QRS Interval [msec], RR Interval [msec], QT Interval [msec], and QTc [msec]) will be summarized by visit using descriptive statistics. An outlier analysis will be performed that will summarize by treatment the frequency and percentage of participants who meet any of the following outlier criteria at each visit:

- QTc interval > 450 msec.
- QTc interval > 480 msec.
- QTc interval > 500 msec.
- QTc interval increases from baseline > 30 msec.
- QTc interval increases from baseline > 60 msec.

This outlier analysis will be repeated summarizing frequency and percentage of participants by treatment who meet any of these outlier criteria at any time during the study.

All ECG parameters, including overall ECG evaluation, will be provided in data listings.

12.5. Physical Examination

A complete physical examination will be performed at Screening and Week 16. A limited physical examination will be conducted at Day 1 and Weeks 4, 8, 12, and 20.

A shift table to demonstrate changes in physical examination from baseline to all post-baseline visits by treatment will be generated.

Physical examination data will be listed.

12.6. The Hospital Anxiety and Depression Scale

The HADS is a patient reported outcome (PRO), comprises 7 questions for anxiety and 7 questions for depression, with each answer being graded from 0 to 3 with a higher score indicating a worse condition. For each group of questions, scores of less than 7 indicate noncases, whereas 8 to 10, 11 to 14, and 15 to 21, indicate mild, moderate, or severe anxiety or depression, respectively. HADS will be collected at different time points as per the SoA in Protocol Section 9.

Actual values and changes from baseline in HADS scores (depression, anxiety, and total) will be summarized by treatment group. A summary table presenting the frequency and percentage of participants by treatment group within categories (< 7, 8 - 10, 11 - 14 and 15 - 21) for anxiety and depression at each visit will be generated. A shift table to demonstrate changes in anxiety total score and depression total score from baseline to all post-baseline visits by treatment will be generated.

HADS scores, questions, and answers will be provided in data listings.

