## 8.3.1 Planned Dosing Schedule – Titration over a Maximum of 2 Weeks

Titration of oral apremilast was shown to improve the GI tolerance and overall acceptability of the drug. Consistent with this approach, this study will titrate the study treatment dose over a maximum period of 2 weeks (see Table 2).

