#### 11.6 The Hospital Anxiety and Depression Scale

The HADS is a PRO, comprises 7 questions for anxiety and 7 questions for depression, with each answer being graded from 0 to 3 with a higher score indicating a worse condition. For each group of questions, scores of 7 or less indicate cases without anxiety or depression, whereas scores of 8 to 10, 11 to 14, and 15 to 21 indicate mild, moderate, and severe cases, respectively. The HADS is one of the tools recommended by the National Institute for Health and Care Excellence for diagnosis of depression and anxiety.

Any patient with a score for depressive symptoms  $\geq 15$  at baseline will not be eligible for enrollment in the study. Patients with a clinically significant worsening of depressive symptoms or new occurrence of clinically significant depression during the study may be referred to a mental health specialist (psychiatrist or clinical psychologist) for further evaluation. After a mental health specialist evaluation, the final decision on restarting or permanently discontinuing study treatment will be at the discretion of the Investigator in consultation with the mental health specialist. These cases should be reported as an AESI. Refer to Section 11.8.2.

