# 14 STATISTICAL ANALYSIS

A statistical analysis plan will be prepared after the protocol is approved. This document will provide further details regarding the definition of analysis variables and analysis methodology to address all study objectives. The statistical analysis plan will serve as a complement to the protocol and supersedes it in case of differences.

The statistical evaluation will be performed using SAS® software version 9.4 or higher (SAS Institute, Cary, NC). All data will be listed, and summary tables will be provided. Summary statistics will be presented by dose group. For continuous variables, data will be summarized with the number of patients, mean, standard deviation, median, minimum, and maximum by treatment group. For categorical variables, data will be tabulated with the number and proportion of patients for each category by treatment group.

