4.1. Brief Description

This multicenter, randomized, double-blind, placebo-controlled, parallel-group, Phase 2b dose-ranging study is designed to assess the efficacy and safety of modified-release orismilast compared with placebo in patients aged at least 18 years with moderate to severe AD. Efficacy and safety outcomes will be evaluated to select an appropriate orismilast dose for subsequent Phase 3 studies. The study will be conducted at approximately 48 centers in Europe and the United States.

After a Screening visit up to 28 days before Baseline, approximately 210 patients will be assigned randomly in a 1:1:1:1 ratio to receive 1 of the 3 orismilast doses (20 mg, 30 mg, or 40 mg) or placebo BID for 16 weeks, with a 4-week follow-up visit. Administration will begin at Baseline with a dose titration period of up to 2 weeks' duration depending on the dose level. The maximum duration of study participation for each patient is approximately 24 weeks.

Patients will be seen at the site at Screening, Baseline (Day 1), and Weeks 1, 2, 4, 8, 12, 16 (EOT visit), and 20 (Follow-up visit, 4 weeks after treatment completion or discontinuation). The visit at Week 1 can be conducted via a telemedicine procedure at the Investigator's discretion.

Patients who have been diagnosed with moderate to severe AD for a minimum of 1 year (before the Screening visit) using the Hanifin and Rajka criteria with affected BSA of at least 10%, Eczema Area and Severity Index (EASI) score of at least 16, and Investigator Global Assessment for Atopic Dermatitis (IGA-AD) grade of at least 3 at the screening and baseline visits will be included in the study. Patients must also have a documented history of inadequate response to treatment with topical medications given for at least 4 weeks (at least 2 weeks for high potency topical corticosteroids), or as labeled, or for whom topical treatments are otherwise medically inadvisable.

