16.2.5.2. Table Conventions

- Units will be included where available
- For categorical parameters, all categories will be presented in the table, even if n=0 for all treatment groups in a given category. For example, the frequency distribution for symptom severity would appear as:

Severity	Ν
Rating	
severe	0
moderate	8
mild	3

Where percentages are presented in these tables, zero percentages will not be presented and so counts of 0 will be presented as 0 and not as 0 (0%).

- An Unknown or Missing category will be added to each parameter for which information is not available for 1 or more patients
- Unless otherwise specified, the estimated mean and median for a set of values will be printed out to 1 more significant digit than the original values, and standard deviations will be printed out to 2 more significant digits than the original values. The minimum and maximum will report the same significant digits as the original values. For example, systolic blood pressure will be presented as follows:

n	XXX
Mean (SD)	xx.x (x.xx)
Median	XX.X
Min, Max	Xx, xx

- P-values will be output in the format: '0.xxx', where xxx is the value rounded to 3 decimal places. Every p-value less than 0.001 will be presented as <0.001. If the p-value are less than 0.0001, then present as <0.0001. If the p-value is returned as >0.999, then present as >0.999
- Percentage values will be printed to one decimal place, in parentheses with no spaces, one space after the count (e.g., 7 (12.8%), 13 (5.4%)). Unless otherwise noted, for all percentages, the number of patients in the analysis population for the treatment group who have an observation will be the denominator. Percentages after zero counts will not be displayed and percentages equating to 100% will be presented as 100%, without decimal places
- Tabular display of data for medical history, prior/concomitant medications, and all tabular displays of adverse event data will be presented by the body system, treatment class, or SOC with the highest occurrence in the active treatment group in decreasing order, assuming all terms are coded. Within the body system, drug class and SOC, medical history (by preferred term), drugs (by ATC3 level), and adverse events (by preferred term) will be displayed in decreasing order. If incidence for more than 1 term is identical, they will then be sorted alphabetically. Missing descriptive statistics or p-values which cannot be estimated will be reported as '-'

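### Descriptive safety outputs: a HADS subscale score of exactly 7 falls in no SAP category, and the AE titration window is 3 weeks although SAP 4.1 and protocol Table 2 give at most 2

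*SAP*

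**What the plan says.** **HADS categories.** SAP 12.6 sets the classes twice. The descriptive text says "scores of less than 7 indicate noncases, whereas 8 to 10" begins the mild class, and the table specification counts patients "within categories (< 7, 8 - 10, 11 - 14 and 15 - 21) for anxiety and depression at each visit". Protocol 11.6 says "scores of 7 or less indicate cases without anxiety or depression", and the scoring key in protocol Appendix 14 also runs the lowest class from 0 to 7. SAP section 14, which lists departures from the protocol, does not mention a change to these classes.

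**Titration window.** SAP 12.1 specifies AE summaries for events "starting within the dose titration period (initial 3 weeks"), and the same 3-week label appears in the titles of Tables 14.3.1.7 and 14.3.1.8 and Listing 16.2.7.3. SAP 4.1 says "Administration will begin at Baseline with a dose titration period of up to 2 weeks". Protocol 8.3.1 says "this study will titrate the study treatment dose over a maximum period of 2 weeks" and refers to Table 2, where every arm is at its target dose from Day 15. Protocol 8.3.2 states that short dose reductions do not lengthen titration. Protocol 6.2 gives a 2-week maximum in one paragraph and up to 3 weeks in the next. SAP 8.8 asks for compliance by titration period (Table 14.1.5.2) and states no window there.

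**The concern.** The protocol gives the SAP precedence: "The statistical analysis plan will serve as a complement to the protocol and supersedes it in case of differences". A slip in the SAP is therefore the controlling rule.

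For HADS, SAP 16.2.5.2 says that, unless otherwise noted, "the number of patients in the analysis population for the treatment group who have an observation will be the denominator", and it reserves the unknown/missing row for information that is not available. A patient who scores 7 has an observation, so that patient would enter the denominator and appear in no row. Percentages would then sum to less than 100% and the lowest class would be understated. HADS is a named safety endpoint, and protocol 4.3.2 lists major depression among the class effects to be monitored, so the category table should account for everyone assessed.

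For titration, events starting on Days 15 to 21 would be reported as titration events although no arm is scheduled to titrate then under Table 2. That week is also the first full-dose week of the 40 mg arm. In addition, the AE and compliance outputs could use the same term for different days.

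**Working it through.** **1. Coverage of the HADS classes.** Each subscale has 7 items graded 0 to 3, so scores are the integers 0 to 21 (22 values).

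| Rule | Lowest class | Other classes | Scores with no class |
|---|---|---|---|
| SAP 12.6 | 0–6 | 8–10, 11–14, 15–21 | 7 |
| Protocol 11.6 | 0–7 | 8–10, 11–14, 15–21 | none |

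Under the SAP, 7 + 3 + 4 + 7 = 21 of the 22 values are covered.

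**2. How many patients this could affect.** The documents give no expected HADS scores. The assumed range is a subscale mean of 3, 5 or 7 with an SD of 3, 3.5 or 4.

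- Normal approximation: P(7) = Φ((7.5 − m)/s) − Φ((6.5 − m)/s). Lowest, m = 3, s = 3: Φ(1.500) − Φ(1.167) = 5.5%. Highest, m = 7, s = 3: Φ(0.167) − Φ(−0.167) = 13.2%.
- Beta-binomial on 0 to 21 with the same mean and SD, which respects the bounds of the scale: lowest 3.1% (m = 3, s = 4), highest 12.7% (m = 7, s = 3).
- Patients per arm: 210/4 = 52.5. Then 52.5 × 0.031 = 1.6 and 52.5 × 0.132 = 6.9, so about 2 to 7 per arm, per visit and per subscale.

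**3. Titration days in protocol Table 2.** Table 2 has one dose on Day 1 and two doses a day after that. The first day on which both doses are at target is Day 8 (20 mg), Day 9 (30 mg) and Day 15 (40 mg). This reproduces the stated 2-week maximum: the longest titration ends on Day 14. Full-dose days in a window ending on Day D are D + 1 minus the first full-dose day.

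| Arm | First full-dose day | Full-dose days in Days 1–21 | Full-dose days in Days 1–14 |
|---|---|---|---|
| 20 mg | 8 | 22 − 8 = 14 (67%) | 15 − 8 = 7 (50%) |
| 30 mg | 9 | 22 − 9 = 13 (62%) | 15 − 9 = 6 (43%) |
| 40 mg | 15 | 22 − 15 = 7 (33%) | 15 − 15 = 0 (0%) |

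Days 15 to 21 make up 7/21 = 33% of the labelled window, and all three active arms are at target throughout them. Moving to 2 weeks removes that week. It does not remove the difference between arms: the gap between 20 mg and 40 mg is 7 full-dose days under either window (14 − 7 and 7 − 0).

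**The case against.** - **Version.** SAP section 2 says it is based on Protocol v2.0, whereas the protocol at hand is v3.0. According to its amendment summary, the section on titration over at most 2 weeks was created, and the section on short dose reductions updated, in that amendment. This stands as a caution about using protocol 8.3.1 and 8.3.2 to explain what the SAP author intended. It does not remove the conflict, because the 2-week and 3-week figures are both in the SAP, and protocol 6.2 carries both as well.
- **The gap may never reach the output.** The shells are a separate document that is not available here, quality control of outputs is planned, and 7 could be read back in from protocol 11.6. That makes short percentages a risk rather than a certainty. The controlling text is still wrong, and nothing in it directs the programmer to the protocol.
- **The 3-week window is explicit.** It is fixed in advance, the same in every arm and printed in the titles, so the tables are reproducible. This is fair. The defect lies in the label and in the contradiction, not in counting early events over 3 weeks.
- **A 2-week window is not clean either.** The second table above confirms this: two arms would still have full-dose days inside a window called titration. For that reason relabelling is as acceptable as shortening.
- **The compliance table has an ordinary reading.** Through SAP 4.1, and with tablet returns starting at the Week 2 visit, it would cover 2 weeks. On that reading, however, it covers different days from the AE tables that use the same term.
- **The HADS range is assumed.** This stands. Also, 52.5 is the number randomised per arm, so counts at later visits are upper estimates.

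**Conclusion.** Both parts hold, and they are worth correcting before programming. The gap at 7 follows directly from the stated classes and needs no assumption. Its size, about 3% to 13% of scores, rests entirely on the assumed means and SDs. The titration conflict is internal to the SAP and also internal to protocol 6.2. Its size, one third of the labelled window, rests on Table 2 as it stands in v3.0.

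The consequences are limited. SAP section 12 plans no inference on safety. HADS raw scores, changes from baseline and listings are unaffected, as are the protocol's thresholds at 15 and above for eligibility and for AEs of special interest. The full-period TEAE tables, the onset-time table (14.3.1.11), the discontinuation plots and every efficacy analysis are also unaffected. Which titration length is correct is not something this review decides; the passages must be reconciled.

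**What to change.** 1. **SAP 12.6:** make the lowest class 0 to 7 in the descriptive text and in the by-category table (14.3.4.4.4.2). Apply it to the shift table (14.3.4.4.4.3) only if its shell uses these classes. All 22 scores then fall in exactly one class.
2. **Titration length:** reconcile 2 against 3 weeks in SAP 4.1, SAP 12.1 and protocol 6.2.
3. **AE outputs (Tables 14.3.1.7 and 14.3.1.8, Listing 16.2.7.3):** either tie the window to the reconciled Table 2 (as it now stands, events starting before Day 15), or keep 3 weeks and describe it as an early treatment period without the word titration.
4. **SAP 8.8:** state the same definition of the titration period for Table 14.1.5.2.

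The cost is wording in the SAP and shells, plus one sentence in protocol 6.2. If the window is shortened, the early-period tables will hold fewer events, and the arms will still differ in full-dose days within it.
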